### **3.0 TTIP-PRO Training, Certification, and Monitoring**

#### **3.1 Finalizing Training Materials**

A training manual was created and utilized for the TTIP-PRO acceptability study; the Peer Interventionists provided positive feedback about the manual (i.e., provided the essential information succinctly) and, thus, we plan to use a version of this manual updated for the present project (e.g., to reference training tapes and other materials not available in the original project, less focus on the TTIP-PRO generated reports and more on an open exchange of information about MAT). Two important elements missing from the acceptability study, which will be established for the present project, are: 1) training files and 2) an assessment of inter-rater reliability for the competence measure.

#### **3.2 Approach for developing training materials**

**1. Creating training files.** The training files will include 4 mock interventions (1 video, 3 audio) and 4 audio recorded interventions with patient volunteers. The 4 mock interventions will be created by ASD staff members acting as patients/interventionists. The mock interventions will include examples of well-done and poorly-done interventions. Since the intervention is delivered via telephone, the intervention for the training files (with the exception of the video file) will be delivered by phone and will be recorded using a combination of an in-ear microphone and a digital voice recorder. MAT patients meeting criteria to serve as a Peer Interventionist and passing certification will be recruited to create 4 audio training files with patient volunteers. Patient volunteers will be recruited from the UCMC ED and will meet the eligibility criteria outlined above (section 1.3) with the additional requirement of agreeing to have their audio recorded intervention used for training purposes.

**2. Inter-rater reliability.** Two TTIP-PRO trainers who have been intimately involved with creating TTIP-PRO will rate two training files. Inter-rater reliability will be measured by intraclass correlation coefficients (ICCs). An ICC in the range of .75 - 1.0 reflects excellent agreement. If the ICC is less than .75 then clarifications will be made to the competence assessment and the trainers will rate two additional training files. This process will be repeated until an ICC greater than .75 is achieved. It is anticipated that the 8 training files will be sufficient for establishing reliability but, if needed, additional training files will be created and rated.

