## **6.0 Study completion time**

An individual participant’s period of time for participation and study completion is approximately 12 months. For an individual Peer Interventionist, the time for participation and completion in the pilot trial is approximately 16 months, which includes the time needed for training and certification and for providing TTIP-PRO sessions during the approximately 14-month enrollment period. It is expected that two Peer Interventionists will help to develop the training materials and also participate in the pilot trial; their time of participation and study completion may take up to 24 months. The present project will take less than 3 years to complete.

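### Aim 1 accepts the competence scale on an ICC point estimate, retested without a cap until it exceeds .75, with no interval and no confirmation afterwards

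*Combined protocol and SAP*

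**What the plan says.** Specific Aim 1 has two parts: making the training files and evaluating the inter-rater reliability of the competence assessment. The method for the second part is in section 3.2 and is repeated in DSMP IV.1.

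- Two trainers, both closely involved in creating TTIP-PRO, rate two files, and agreement is measured by an ICC.
- "If the ICC is less than .75 then clarifications will be made to the competence assessment and the trainers will rate two additional training files". Then: "This process will be repeated until an ICC greater than .75 is achieved".
- The benchmark is stated as "An ICC in the range of .75 - 1.0 reflects excellent agreement".
- On quantity: "It is anticipated that the 8 training files will be sufficient for establishing reliability", but "if needed, additional training files will be created and rated".
- On the material: "The mock interventions will include examples of well-done and poorly-done interventions". The other four files come from peers "passing certification will be recruited to create 4 audio training files with patient volunteers", and section 6.0 expects that "two Peer Interventionists will help to develop the training materials".

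Section 3.3 describes the scale: six abilities, each scored on three points, with a 1 needed on at least five. Section 3.4 uses the same assessment for every trial session, and DSMP IV.1 has each session rated by one of the two trainers.

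The plan does not state the ICC form (single or average measure, one-way or two-way), the rating unit (item or file total), whether files are pooled over rounds, which files form a pair, or a maximum number of rounds. Section 5.2 promises confidence intervals for treatment effects only.

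**The concern.** A rule that repeats a noisy test until it passes has one possible ending. The value that ends it has been selected for being high, and here nothing follows to check it. Later trial data cannot do so, because each session has a single rater. For the same reason, single-rater reliability is the quantity that matters in use.

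At stake is whether the Aim 1 conclusion, and the top agreement label attached to it, can be relied on. The scale helps decide who is certified and when a peer needs retraining or must stop, and a full-scale trial would inherit it.

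**Working it through.** The plan gives no precision or error rate for this step, so there is no figure of its own to reproduce.

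**Inputs from the plan.** Two raters; two files per round; threshold .75; eight files, hence 8/2 = 4 planned rounds; six abilities, hence 6 × 2 = 12 item-by-file pairs per round if items are the unit, or 2 file totals if files are.

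**Assumptions.** The true single-rater ICC (ρ) is not given and is varied. Scores are taken as normal. Item pairs are treated as independent, which is optimistic because ratings of one recording tend to move together.

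**Formula.** With two raters, single-rater ICC = (F − 1)/(F + 1), so ICC > .75 means F > 7. For n units, the chance of passing one round is p = P[F(n − 1, d) > 7(1 − ρ)/(1 + ρ)], with d = n (one-way) or n − 1 (two-way consistency). With fresh files each round and no gain from clarification, the chance of passing within four rounds is 1 − (1 − p)^4.

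**Example, ρ = .6.** The cut is 7 × .4/1.6 = 1.75.
- 12 item pairs: p = .175 (one-way) or .184 (two-way). Four rounds: 1 − .825^4 = .54, or .56.
- 2 file totals: p = .317 or .412. Four rounds: 1 − .683^4 = .78, or .88.

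| Pass within four rounds, no pooling | 12 item pairs | 2 file totals |
|---|---|---|
| ρ = 0 | under 1% | 40–65% |
| ρ = .5 | 28–31% | 71–84% |
| ρ = .6 | 54–56% | 78–88% |

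Since p > 0 in every case, the chance of an eventual pass tends to 1 as rounds are added.

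**Pooling.** If each look used all files rated so far, simulation with the one-way ICC (20,000 replicates) gives a pass within four looks at ρ = .6 of about 22% (item pairs) or 50% (file totals). At ρ = 0 it gives 0.1% or 14%.

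**Average-measure form.** An average-measure .75 equals a single-rater .75/(2 − .75) = .60. On item pairs without pooling, a true single-rater .6 then passes within four rounds about 94% of the time.

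**Interval at an observed .75 (one-way, F = 7).** Divide F by the 97.5% and 2.5% points of F(n − 1, n), then convert back.
- 12 pairs: lower 7/3.32 = 2.11, giving 1.11/3.11 = .36; upper 7/.292 = 24.0, giving 23.0/25.0 = .92.
- 2 file totals: lower 7/38.5 = .182, giving −.818/1.182 = −.69; upper 1.00.

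**If clarification works.** Assume ρ rises .5, .6, .7, .8 over the rounds (12 pairs, one-way). First passes by round are .081, .161, .273 and .319, total .834. Passes at .6 or lower: .242/.834 = 29%. Passes at .7 or lower: .515/.834 = 62%. The two-way form gives a total of .839, with 30% and 63%.

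**The case against.** The strongest reply is that this is rater calibration in a pilot. Revising a scale and trying it on new recordings is normal development, and section 3.2 does test each clarified version on additional files. Certification also requires the manual, the training session, a practice intervention and a 90% OOTAS score. Every session is rated, with consequences for poor performance. All of this stands. The fault is not the iteration, but the absence of any check outside it.

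Three stronger readings might be inferred, and the documents do not support them.

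- *Acceptance always rests on two recordings.* That is certain for round one. For later rounds it is the natural reading, because the scale has changed, but pooling is neither stated nor excluded. Pooling lowers the pass rates without supplying an interval, a cap or a confirmation.
- *Raters agreeing only by chance would probably pass.* That is a real risk only with file totals as the unit. On independent item pairs it is under 1%. The plan defines neither unit, so neither result can be presented as the plan's own.
- *Only the passing value will be reported.* No passage says which ICC will be reported. It is simply the natural result unless every round is shown.

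The rising-ICC path is assumed, and its message depends on the cut: .7 is close to .75, and the share of passes at .6 or lower is about half the share at .7 or lower.

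**Conclusion.** The point holds and is worth correcting. As written, the reliability evaluation in Aim 1 can end only in a pass, on a point estimate with no planned interval and no later double rating. The size is conditional on the ICC form, the rating unit, pooling and any gain from clarification. The most realistic risk is moderate agreement accepted under the plan's top label.

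The reach is limited to Aim 1 and to the certification and fidelity ratings. A reader might infer damage to the trial's efficacy results, but no efficacy, mediation or exploratory analysis in section 5.2 uses the scale.

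**What to change.** Change section 3.2 and DSMP IV.1 together.

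1. Keep the rounds for clarifying the scale, and report the ICC with a 95% CI from every round.
2. Freeze the scale. Have the same two trainers independently rate, once, a number and mix of recordings fixed in advance. The mix matters because an ICC depends on the spread of quality in the recordings.
3. Use files that played no part in revision, or extra staff-made mock files, since 3.2 already allows more files. If a file used for revision is re-rated, say so and show the result with and without it.
4. Report the single-rater ICC with its form, unit and 95% CI as the Aim 1 result, whatever its value. Add percent agreement per ability and on the pass/fail call, because an ICC is unstable when nearly every rating is a 1. Do not call agreement excellent on a point estimate alone.
5. If the scale is revised after that, the frozen-scale result stands. The revised version is described as unconfirmed unless it is rated once on new files.

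**Limits to state.** A single rating of eight recordings remains imprecise:

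| Unit | 95% CI at observed .75 | Exceeds .75 at true .6 | at .8 | at .9 |
|---|---|---|---|---|
| 8 file totals | .21 to .94 | 22–24% | about 62% | 89–90% |
| 48 independent item pairs (8 × 6) | .60 to .85 | about 3% | about 80% | over 99% |

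These figures assume no carry-over from earlier ratings.

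**Cost.** Eight recordings × about 20 minutes × 2 trainers = 320 minutes, or about 5–6 trainer-hours including some slack, plus scoring. After one, two, three or four rounds, 6, 4, 2 or 0 of the eight files remain unused, so a fresh group of eight would need 2, 4, 6 or 8 extra mock recordings. The Aim 1 conclusion becomes more modest.

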### **3.3 Training and Certification of Peer Interventionists**

Potential Peer Interventionists will need to complete training and certification prior to being assigned participants. The process of becoming a certified Peer Interventionist includes the following:

1. Reading the TTIP-PRO Peer Interventionist Manual
2. Attending a training session on the TTIP-PRO Intervention
3. Completing a practice intervention with the assigned trainer.
4. Completing a blank copy of the OOTAS – the trainee needs to get at least 90% of the questions correct to “pass.” The OOTAS may be taken more than once.
5. Successfully completing a “mock” intervention. This entails providing the intervention to a person who is not a patient. The trainee’s performance will be rated by the trainer using a 3-point scale (1- Meets expectations, 2-Needs improvement, 3-Expectations not met and additional training required). To be certified, the trainee needs to receive a “1” on at least 5 of the 6 abilities assessed:
  1. Ability to provide information while maintaining a conversational tone
  2. Ability to successfully complete the intervention within 20 minutes
  3. Ability to listen
  4. Sufficient familiarity with correct information about OOD and MAT to answer the participant’s questions
  5. Ability to remain non-judgmental and encouraging
  6. Ability to avoid confrontation

### **3.4 Fidelity and Adherence Monitoring**

All TTIP-PRO interventions will be audio recorded and rated for adherence/fidelity using the same assessment as that used for certification. Any instance of falling below certification criteria will result in additional training or discontinuation from the trial depending on the nature of the problematic performance.

## 4.0 Study Procedures

### 4.1 Schedule of Assessments and Procedures

Table 1 provides an overview of the participant procedures and assessments. Table 2 provides an overview of the assessments that involve the Peer Interventionists.

**Table 1. Overview of Study Assessments and Procedures for Study Participants**

Assessment/Procedure	Scr/Base/ Random	TTIP-PRO Intervention	3 WK FU call	3 Mo FU visit	6 Mo FU visit	12 Mo FU visit
Completed by	ASD RA	Peer Interventionist	ASD RA	ASD RA	ASD RA	ASD RA
Screening Assessments						
Informed consent	X					
Releases of information	X					
Demographics	X					
NIDA modified ASSIST	X					
Efficacy Measures						
MAT Entry Tracking				X	X	X
Opioid Overdose Tracking				X	X	X
Urine drug screen	X			X	X	X
Time line follow-back	X			X	X	X
Safety Measures						
Adverse Events			X	X	X	X
Process Measures						
HOPI			X			
OOTAS	X		X			
Barriers to Treatment	X		X			
Thoughts about abstinence	X		X			
Other Assessments						
Locator Information Form	X			X	X	
PORS	X					X
Utilization of NARCAN®				X	X	X
Interventions						
Provision of OOD and MAT information and NARCAN® Nasal Spray kit (all participants)	X					
TTIP-PRO Intervention		~ 2 weeks post-enroll				
Compensation	\$50		\$20	\$50	\$50	\$50

[figure not shown]
**Table 2: Peer Interventionist Assessments**

Assessment	Purpose	Collection Schedule
Demographics and eligibility	Document Peer Interventionist study eligibility	Screening/enrollment
The OOTAS –Peer Interventionist Certification	Helps to ensure intervention quality	During certification
Rating of TTIP-PRO sessions	Helps to ensure intervention quality	During certification and throughout the trial
Peer Volunteer Experience Questionnaire (PVEQ)	To obtain feedback on providing TTIP-PRO	End of study participation
PROMIS 10-item measure for Global Health	To assess physical, mental, and social health	Screening/enrollment and every 4 months during participation in pilot trial
Adverse Events	Safety	After every TTIP-PRO session

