#### **1.2 Number of sites and participants**

This is a single site study; all data will be collected at the University of Cincinnati. This project includes two types of participants: 1) the participants who may receive the TTIP-PRO intervention, referred to as participants, and 2) the participants who will serve as Peer Interventionists. Participants will be recruited to develop training audio files until 4 training tapes are obtained; all of these “training” participants will receive the TTIP-PRO intervention. Approximately 80 participants will be randomized into the pilot efficacy trial. Approximately 15 Peer Interventionists will participate.

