#### **Exclusion Criteria:**

1. Unwilling to sign a release of information (ROI) to allow research staff to confirm pertinent eligibility criteria and to monitor clinical status with UC ASD (i.e., UC Health/UCPC) MAT clinical staff;
2. Clinical staff from their program have significant concerns about their participation;
3. Unwilling to have their sessions audio recorded and assessed by a TTIP-PRO trainer;
4. Specific plan to leave the UC ASD (i.e., UC Health/UCPC) MAT program within the next 6 months.

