#### **1.4.2 Peer Interventionist Assessments**

Demographics -This assessment includes questions about the Peer Interventionist's ethnicity, age, and sex.

Peer Volunteer Experience Questionnaire (PVEQ) – The PVEQ was developed by Dennis and colleagues to obtain feedback from peer volunteers delivering an intervention for post-partum depression. Three sections of the PVEQ are relevant for TTIP-PRO and will be used to obtain feedback on: 1) the training and certification process; 2) interactions with participants; and 3) the personal effects of being a Peer Interventionist (e.g., benefits and drawbacks of being a Peer Interventionist). An additional item will be included to assess the Peer Interventionist's satisfaction with his/her experience, rated on a 5-point scale (1-very dissatisfied, 2-dissatisfied, 3-neither satisfied or dissatisfied, 4- satisfied, 5-very satisfied).

Global Health will be assessed with the PROMIS 10-item measure for Global Health, which briefly but comprehensively assesses physical, mental, and social health; this is a reliable (Cronbach's  $\alpha > 0.80$ ) measure with demonstrated construct validity. The interventionists will complete this measure, used to assess positive and negative outcomes, prior to being assigned participants (baseline), every 4 months during the approximately 14 month enrollment period, and after the last TTIP-PRO intervention has been provided.

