### **1.4.3 Collection and reporting of adverse events (AEs) and serious adverse events (SAEs)**

In general, the risks associated with trials employing behavioral interventions are presumed minimal relative to those evaluating pharmacologic interventions. Based on the TTIP-PRO acceptability study the risk from TTIP-PRO is low. Still, for the present trial, the population studied may possibly be at higher risk given the nature of the disorder and the population. Thus, the following events, which are not defined as SAEs, will be tracked on an AE CRF for participants and Peer Interventionists:

1. Suicidal ideation
2. Homicidal ideation

In addition, the following events will be tracked on an AE CRF for the Peer Interventionists:

1. Discharge from MAT program for any reason
2. Illicit opioid use
3. Other clinical deterioration as reported by clinic staff

For TTIP-PRO, which is a behavioral trial, the RA is primarily responsible for assessing the occurrence of AEs/SAEs with oversight by the Study Medical Monitor and PI. For Participants, the RA will query about how s/he has been feeling since the last visit (i.e., at the follow-up phone call in week 3 and in-person visits at 3, 6-, and 12-months following enrollment). For Peer Interventionists, the RA will query about how s/he has been feeling following the delivery of each TTIP-PRO intervention. All AEs/SAEs occurring during the course of the clinical trial will be collected, documented, and reported by the investigator or sub-investigators in accordance with reporting requirements. [name] or the designated study physician will assess the severity, causality and outcome of all AEs and SAEs. It will also be Drs. [name]', [name]'s, and [name]'s responsibility to manage all AEs and SAEs and to make referrals for appropriate care, as necessary. All SAEs will be reported to the University of Cincinnati Institutional Review Board and the NIDA project officer within 72 hours of their discovery. All subject information will be de-identified when reporting serious adverse events.

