### **1.5 Randomization Plan**

Eligible participants will be randomized in a 1:1 ratio to the control or experimental arms. The randomization sequence will be unknown to the research staff.

[figure not shown]

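### Peer Interventionists are directly asked about adverse events only after each session, about 2.7 times each, and the contacts already planned every four months carry no such query

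*Combined protocol and SAP*

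**What the plan says.** Table 2 gives the collection schedule for peer AEs as "After every TTIP-PRO session". Section 1.4.3 states that for peers "the RA will query about how s/he has been feeling following the delivery of each TTIP-PRO intervention", and DSMP section VI.2 repeats it. Five kinds of event go on the peer AE form: suicidal ideation, homicidal ideation, discharge from the MAT program, illicit opioid use, and other deterioration reported by clinic staff.

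Section G and DSMP section VI.1 name two risks for peers, breach of confidentiality and relapse. They also describe a second detection route. The peer agrees to continuing exchange of information between the research team and the treatment providers, the two teams share a location and meet daily, and clinic staff are told to report deterioration. A peer who will not sign the release for this is excluded (section 1.3.2).

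Section 6.0 says that for a peer "the time for participation and completion in the pilot trial is approximately 16 months", and up to 24 months for the two who also help with the training materials.

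Other contacts with peers exist. Section 1.4.2 has the PROMIS Global Health measure at baseline, then "every 4 months during the approximately 14 month enrollment period, and after the last TTIP-PRO intervention has been provided". Table 2 lists the PROMIS at enrollment and every four months, without the collection after the last intervention, and the PVEQ at the end of participation. No AE query is attached to any of these.

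**The concern.** Direct questioning is triggered only by delivering a session. A peer with few sessions is asked few times, however long he or she stays in the study, and a peer with none is never asked. Trial participants, by contrast, are asked at four fixed contacts (the week-3 call and the 3-, 6- and 12-month visits) how they have felt since the previous one. The peer query has no calendar and no stated look-back period.

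Two kinds of event are exposed: ideation, which clinic staff have no specific instruction to pass on, and opioid use that the clinic does not know about. For both, nothing is scheduled between sessions or after the final post-session query. The DSMB reviews AE data every six months (DSMP section VIII.2). If the peer record is thin, the absence of reported events is weak reassurance in a pilot meant to prepare for a full-scale trial.

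**Working it through.** The documents give no number of sessions or AE queries per peer, so there is no stated figure to reproduce. The steps below are direct arithmetic.

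**Inputs**
- Section 1.2: "Approximately 80 participants will be randomized into the pilot efficacy trial".
- Section 1.5: "Eligible participants will be randomized in a 1:1 ratio to the control or experimental arms". So about 80 × 1/2 = 40 are assigned to TTIP-PRO.
- Section 1.2: "Approximately 15 Peer Interventionists will participate".
- Duration: about 14 months of enrollment (section 1.4.2) and about 16 months of peer participation (section 6.0).

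**Current schedule**
- Queries per peer = sessions per peer = 40/15 = 2.67, assuming even allocation.
- If the number of peers differed (assumed range): 40/12 = 3.3 and 40/18 = 2.2. Adding the four training-tape sessions of section 1.2 gives 44/15 = 2.9.
- Mean spacing: 14/2.67 = 5.25 months, or 16/2.67 = 6.0 months. Against six-monthly DSMB reviews, that is about one query per peer per review.

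**Uneven allocation.** If the 40 sessions fell at random across 15 peers (an assumption, since no assignment rule is given):
- P(no session) = (14/15)^40 = 0.063.
- P(at most one) = 0.063 + 40 × (1/15) × (14/15)^39 = 0.244.
- Expected among 15 peers: 15 × 0.063 = about 1 never asked, and 15 × 0.244 = about 3.7 asked at most once.

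**Time after the last query.** With k sessions placed at random over 14 months (an assumption), the expected time from the last session to the end of enrollment is 14/(k+1): 14/3 = 4.7 months for k = 2 and 14/4 = 3.5 months for k = 3.

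**With a query at the existing contacts**
- PROMIS at months 4, 8 and 12: 2.67 + 3 = 5.7 queries per peer.
- Plus the PROMIS after the last intervention: 6.7.
- Plus the PVEQ, if it is a separate contact: 7.7.
- Ratios to the current schedule: 5.67/2.67 = 2.1, 6.67/2.67 = 2.5 and 7.67/2.67 = 2.9.
- The longest planned interval up to month 12 becomes about 4 months, whatever the session load.

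**The case against.** The strongest reply is that the session query is not the main safeguard against relapse. Release-based monitoring with the co-located clinic is. It is not tied to sessions, it runs between and after them while the peer is enrolled, and it feeds the AE form directly. This stands, and it rules out saying that relapse between sessions goes uncollected. It does not fully close the gap. The route depends on what the clinic learns, has no stated reporting interval or end date, and has no specific path for suicidal or homicidal ideation.

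Tying queries to sessions also has some logic, since the stated hazard is exposure to active users during the call. The PROMIS and PVEQ also look for negative effects, though neither is linked to the AE form. No peer AE rate is a planned estimate; the peer analyses in section 5.2 are certification within the expected time and satisfaction.

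Four stronger readings are tempting, and the documents do not support them:
- *Peers are not asked after their last session.* Table 2 and section 1.4.3 cover every session, including the last. What is missing is any later query.
- *The query comes too early to catch a relapse caused by the call.* The text fixes neither its timing nor its look-back.
- *Clinic cover lapses after six months.* The exclusion concerning a plan to leave the "MAT program within the next 6 months" screens for a specific intention; it does not imply that peers will leave. Discharge is itself a tracked event, and the documents do not say that a discharged peer would continue in the study.
- *The peer AE rate will be biased low.* Incomplete ascertainment is possible, but a definite bias is not shown.

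**Conclusion.** The point holds as a limited weakness in scheduled ascertainment. Peers are directly asked about AEs about 2.7 times each over 14 to 16 months, and the number depends on workload. The contacts already planned on a calendar are not used for the purpose. Clinic reporting covers much of the relapse risk, so the supported conclusion is that peer AEs may be incompletely ascertained, mainly ideation and opioid use unknown to the clinic.

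The figure of 2.7 assumes about 40 sessions, 15 peers and even allocation; the spacing also assumes that peers are active throughout. The gain from the fix assumes contacts at months 4, 8 and 12. It is nearer 5.7 than 6.7 if the PROMIS after the last intervention is taken together with the final post-session query. Separately, Table 2 and section 1.4.2 disagree on whether that PROMIS is collected. This is a worthwhile low-cost improvement and does not threaten the trial's main results.

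**What to change.** In Table 2, section 1.4.3 and DSMP section VI.2, keep the query after each session and add a peer AE query at each four-monthly PROMIS contact, at the PROMIS after the last intervention, and at the PVEQ. Word every peer query to cover the whole interval since the previous one and to ask about each listed event, including whether the peer is still in the UC ASD program. Add the PROMIS after the last intervention to Table 2 so that it agrees with section 1.4.2. Decisions on discontinuing a peer stay with the clinical team and the investigator.

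The cost is a few extra questions for about 15 people at contacts already planned, and edits to one table and two sections. No new visits or staff are needed.
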